12.1 Sample size and analysis

The primary hypothesis is that ^{99m}Tc -rhAnnexin V-128 SPECT carotid imaging can detect apoptosis. We anticipate that the prevalence of positive ^{99m}Tc -rhAnnexin V-128 SPECT carotid scans will be about 0.3 to 0.5 of the patients. A sample size of 30 patients produces a 95% confidence interval with a precision of about 0.17 to 0.20 when the estimated proportion is 0.3 to 0.5. Sample size was also estimated for the comparison of ^{99m}Tc -rh-Annexin-V 128 uptake in asymptomatic patients with carotid disease versus normals using a 5% significance level and power of 95%. The measured neck uptake in 12 normals was $0.8 \pm 0.27\%$ ID/gm in the Phase I study. Assuming a similar SD of 0.27% ID/gm in the patients and a minimal clinically important difference (MCID) of 50% or a change of 0.4 in uptake, the required sample size is 9 normals and 25 patients. Allowing for attrition, we plan to recruit 10 normals and 35 patients.

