4.3.5 Planned sample size

The primary hypothesis is that ^{99m}Tc-rhAnnexin V-128 carotid imaging can detect apoptosis. We anticipate that the prevalence of positive ^{99m}Tc-rhAnnexin V-128 carotid scans will be about 0.3 to 0.5 of the patients. A sample size of 30 patients produces a 95% confidence interval with a precision of about 0.17 to 0.20 when the estimated proportion is 0.3 to 0.5. Sample size was also estimated for the comparison of ^{99m}Tc-rhAnnexin V-128 uptake in asymptomatic or symptomatic with TIA patients with carotid disease versus normals using a 5% significance level and power of 95%. The measured neck uptake in 12 normals was 0.8 ± 0.27% ID/gm in the Phase I study. Assuming a similar SD of 0.27% ID/gm in the patients and a minimal clinically important difference (MCID) of

²Anti-rhAnnexin V-128 IgG and IgM antibodies will be quantified in serum samples by ELISA. For this purpose 10 mL blood samples will be collected at screening and Day 30 (±3 days) post administration of investigation product. Serum will be prepared, divided into six aliquots and frozen (-80°C). Three out of six serum samples per time-point will then be shipped to the central laboratory.

³Within 8 weeks prior to ^{99m}Tc-rhAnnexin V-128 SPECT imaging.

Version: 01 Page: **22 of 167**

50% or a change of 0.4 in uptake, the required sample size is 9 normals and 25 patients. Allowing for attrition, we plan to recruit 10 normals and 35 patients.

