6.1.2.3 Secondary endpoints

The secondary endpoints of Phase II and the related statistical analysis are:

- Descriptive statistics of ^{99m}Tc-rhAnnexin V-128 uptake in patients vs control participants will be presented by areas of interest (left carotid, right carotid, thoracic aorta, abdominal aorta and aortic arch) and by time points to assess the background uptake profile and the pathologic profile. Comparison of uptake in patients vs controls at each timepoint will be explored by the most appropriate test i.e. two sample t-test.
- The relationship between carotid uptake (separately for left and right) and ultrasound grade of plaque echolucency/echogenicity (1 echolucent, 2 predominantly echolucent, 3 predominantly echogenic, 4 echogenic) will be assessed for all patients using box plots and

Version: 01 Page: **26 of 167**

summaries of uptakes by the levels of echolucency/echogenicity for each time point. Only carotids with stenosis (defined as \geq 50% as per protocol) will be included in this analysis (i.e. a patient with only 1 carotid with stenosis \geq 50% will contribute data for that carotid uptake value and the associated plaque echolucency/echogenicity value for the same carotid, patients with stenosis in both carotids will contribute data on uptake and echolucency/echogenicity for each of their carotids).

Association between carotid and aortic uptake will be assessed for patients and controls, by time
point, using scatter plots. All carotids with ≥ 50% stenosis (as described above) will be included
in this plot, and different colours/symbols will be used for left and right carotid results. If further
investigation is considered appropriate, the correlation coefficients (Pearson's or Spearman's)
within left carotids and right carotids separately will be calculated.

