6.1.20 Significance testing and estimation

All statistical tests will be two-sided at the 5% level of significance.

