10.3 Tables index

14. TABLES, FIGURES AND GRAPHS

14.1 DEMOGRAPHIC DATA

Table 14.1.1: Subject Disposition

Table 14.1.2: Analysis Populations

Table 14.1.3: Protocol Deviations

Table 14.1.4.1: Demographics – FAS Population

Table 14.1.5.1: Carotid Ultrasound – FAS Population

Confidential

Page: **38 of 167**

Table	14.1.6.1:	Medical History and Associated Pathologies – Safety Population
Table	14.1.7.1:	Prior Medications or Non-Drug Tharapies – Safety Population
Table	14.1.7.2:	Prior and Concomitant Medications or Non-Drug Therapies – Safety Population
Table	14.1.8.1:	Study Drug Administration – Safety Population
14.2 EFFICACY	DATA	
Table	14.2.1.1:	Carotid and Aorta Imaging Assessment – Prevalence of Positive Scans – FAS Population
Table	14.2.1.2:	Carotid and Aorta Imaging Assessment – Prevalence of Positive Scans – PP Population
Table	14.2.1.3:	Patient Carotid and Aorta Imaging Assessment – Comparison between time point – FAS Population
Table	14.2.1.4:	Left Carotid Uptake Imaging Assessment – Target to Background Ratio (TBR) – FAS Population
Table	14.2.1.5:	Right Carotid Uptake Imaging Assessment – Target to Background Ratio (TBR) – FAS Population
Table	14.2.1.6:	Thoracic Aorta Uptake Imaging Assessment – Target to Background Ratio (TBR) – FAS Population
Table	14.2.1.7:	Abdominal Aorta Uptake Imaging Assessment – Target to Background Ratio (TBR) – FAS Population
Table	14.2.1.8:	Aortic Arch Uptake Imaging Assessment – Target to Background Ratio (TBR) – FAS Population
Table	14.2.1.9:	Left Carotid Uptake Imaging Assessment by ultrasound grade of plaque echolucency/echogenicity – Target to Background Ratio (TBR) – Patients - FAS Population
Table	14.2.1.10:	Right Carotid Uptake Imaging Assessment by ultrasound grade of plaque echolucency/echogenicity – Target to Background Ratio (TBR) – Patients - FAS Population

Version: 01

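### The 95% power stated for patients versus controls was computed on Phase I neck uptake in %ID/g, but the SAP's patient-control t-tests are on per-vessel target-to-background ratio, so it describes none of them

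*Protocol*

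**What the plan says.** Protocol 12.1 sizes the study twice: once for the precision of the prevalence estimate, and once for a comparison of uptake in patients "versus normals using a 5% significance level and power of 95" per cent. The inputs to the second calculation come from Phase I: "The measured neck uptake in 12 normals was 0.8 ± 0.27% ID/gm in the Phase I study" (SAP 4.3.5, same figures in Protocol 12.1). The calculation continues "Assuming a similar SD of 0.27% ID/gm in the patients and a minimal clinically important difference (MCID) of 50% or a change of 0.4", and concludes that "the required sample size is 9 normals and 25 patients". Recruitment is set at 10 and 35 to allow for attrition.

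SAP 6.1.2.3 plans the comparison by area of interest (left carotid, right carotid, thoracic aorta, abdominal aorta, aortic arch) and by time point. It says the comparison "will be explored by the most appropriate test i.e. two sample t-test". It speaks only of uptake and names no unit. The unit appears in the table shells, for example Table 14.2.1.4: "Left Carotid Uptake Imaging Assessment – Target to Background Ratio (TBR) – FAS Population". Tables 14.2.1.5 to 14.2.1.8 follow the same pattern for the other four vessels. Each carries a t-test p-value at 60 and at 120 minutes.

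SAP section 8 records no changes from the protocol.

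**The concern.** A power statement holds for one variable, one SD and one difference. Here the variable that was sized (neck uptake, %ID/g) is not the variable that will be tested (TBR in a single vessel). TBR is a ratio with its own units and variance, and its spread depends on the background region as well as the target. Neither document says which region supplies the background. An SD of 0.27 and a difference of 0.4 in %ID/g therefore say nothing about TBR.

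What is at stake is how a null result is read. A non-significant p-value in one of these tables would sit beside a claimed 95% power. It could be taken to rule out a meaningful difference, in a study that the protocol says should inform later confirmatory trials.

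**Working it through.** **1. Inputs.** Control mean 0.8, SD 0.27 in both groups, difference 0.4 (50% of 0.8), 5% level, 95% power, 9 versus 25 (Protocol 12.1, SAP 4.3.5). The sample-size text does not give sidedness. SAP 6.1.20 does: "All statistical tests will be two-sided at the 5% level of significance".

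**2. Reproducing the plan's figure.** With allocation ratio r = 25/9, the normal-approximation number of controls is (1.960 + 1.645)² × (1 + 1/r) × 0.27²/0.4² = 12.995 × 1.36 × 0.4556 = 8.05, rounded up to 9. Patients are then 9 × 25/9 = 25. The one-sided version gives 7 controls, so the two-sided formula is the one that matches.

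Noncentral-t power, with noncentrality 0.4 / (0.27 × √(1/n₁ + 1/n₂)):

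- 9 v 25: 0.4 / (0.27 × 0.3887) = 3.81 on 32 df, power 95.9%.
- 10 v 35: 0.4 / (0.27 × 0.3586) = 4.13 on 43 df, power 98.1%.

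The calculation is correct for what it calculates.

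**3. What was sized against what is tested.**

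| | Sized (Protocol 12.1, SAP 4.3.5) | Tested (SAP Tables 14.2.1.4 to 14.2.1.8) |
|---|---|---|
| Region | Neck | Five separate vessels |
| Unit | %ID/g | TBR |
| Time point | Not stated | 60 and 120 min |
| SD | 0.27 | None given |
| Minimal difference | 0.4 | None given |
| Number of tests | One | 5 × 2 = 10 |

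No row of the right-hand column can be filled from the left, because neither document gives a conversion. Listing 16.2.6.2, the uptake listing, also shows only TBR.

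**4. What the TBR tests would need.** In SD units, the sizing assumes 0.4/0.27 = 1.48. For 95% power, the difference has to be about 1.45 SD at 9 v 25, or 1.32 SD at 10 v 35. Whether per-vessel TBR separates the groups by that much cannot be judged from the documents.

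**5. Which arteries enter the carotid tests.** Inclusion needs at least 50% stenosis in at least one carotid (Protocol 8.1). The echogenicity tables (14.2.1.9 and 14.2.1.10) are limited to stenotic carotids by footnote. The patient-control tables for left and right carotid (14.2.1.4 and 14.2.1.5) carry no such limit. Each of 35 patients contributes one or two stenotic carotids out of two, so between 35 and 70 of 70 carotids (50% to 100%) are stenotic. If non-stenotic arteries took up tracer at control level, which the documents do not say, the mean difference averaged over the two sides would be 0.5 to 1 times the difference in stenotic arteries. The split by side is unknown, and an artery below 50% stenosis may still hold plaque, so this shows a direction and not an estimate.

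**The case against.** **The comparison is exploratory.** Protocol 12.4 describes inferential statistics as mainly explorative, and SAP 6.1.2.3 lists this comparison as secondary. The Phase II primary endpoint is a prevalence with an exact confidence interval, which is unaffected. This stands, and it limits the seriousness of the point. It does not make the power statement true of the tests that will be run.

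**The SAP text says uptake, not TBR.** An analyst could test activity concentration and still comply with 6.1.2.3. But the uptake shells and the uptake listing contain TBR only, so the plan as specified produces no such test.

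**Testing carotid %ID/g would not restore the 95%.** This also stands. The Phase I SD is for neck uptake, not for a volume of interest on one carotid. The unit would match and the region would not.

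**A stronger reading that fails.** A reader might infer that the power calculation contradicts the same section, which expects that positive "SPECT carotid scans will be about 0.3 to 0.5 of the patients", since a mean shift of 0.4 seems to require every patient to be abnormal. The documents do not support this. A positive scan is a classification against the control database (Protocol 10.3, SAP 6.1.2.2), with no numerical cut-off given. If every patient shifted by 0.4 with SD 0.27, the share above control mean + k SD would be 1 − Φ(k − 1.48): 30% at k = 2, 32% at 1.96 and 44% at 1.645, all within the expected range. Stricter cut-offs give less (15% at 2.5, 6% at 3). The alternative model, in which only 30% to 50% of patients shift by 0.4 and the rest stay at control level, makes only 11% to 16% positive at k = 2 (0.3 × 0.302 + 0.7 × 0.023 = 0.107; 0.5 × 0.302 + 0.5 × 0.023 = 0.162). It therefore fits the stated prevalence worse at that cut-off. Low power figures built on that all-or-none model, or on a guessed TBR SD, should not be attributed to this design.

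**Conclusion.** The point holds as a mismatch between the variable sized and the variable tested. The 9 v 25 arithmetic is sound at 95.9%, and 98.1% at 10 v 35. It applies only to a mean difference of 0.4 with SD 0.27 in neck %ID/g. None of the ten planned patient-control t-tests is on that variable. Their power is unknown from the documents; it has not been shown to be low. The absence of a stenosis restriction in the two carotid tables is a second reason why the sizing may not carry over, of unknown size.

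This rests on taking the SAP table shells as the planned analysis, and on the protocol and SAP alone. The Phase I report and the DMC charter were not available and might hold TBR data. The consequence is a misdescribed property of a secondary, exploratory comparison. It is worth correcting because the correction is cheap and the statement would otherwise frame how null results are read.

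**What to change.** - In Protocol 12.1 and SAP 4.3.5, state that the 95% applies only to a mean difference of 0.4 with SD 0.27 in neck %ID/g, and that no power is claimed for the per-vessel TBR t-tests. Alternatively, drop the power claim for this comparison.
- In SAP 6.1.2.3, and in the shells for Tables 14.2.1.4 and 14.2.1.5, run the patient-control t-test on carotid activity concentration (%ID/g), with TBR alongside. SAP 4.3.3.3 and 6.1.2.2 already call for activity concentration to be determined. Note beside it that the Phase I SD is for neck uptake and not for a carotid volume of interest.
- In the same two tables, say whether non-stenotic carotids are meant to be included, since the echogenicity tables exclude them.

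The cost is a less favourable power statement and one extra set of columns, including activity concentration in the uptake data that the sponsor supplies for Listing 16.2.6.2. No additional patients, scans or visits are needed.

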12.2 General statistical considerations

Statistical methods will be detailed in the Sponsor statistical analysis plan.

Continuous variables will be presented as number of non-missing values, mean, standard deviation, median, minimum, maximum and quartiles. For categorical variables, descriptive statistics will include counts and percentages per category. Confidence intervals will be computed when appropriate. Continuous variables will be compared using the most appropriate test such as paired analysis Mann-Whitney-Wilcoxon U test or paired analysis student-t test. Proportions will be compared using the most appropriate test such as Chi squared test, fisher exact test or McNemar test. Pearson's or Spearman linear regression analysis will be used to calculate the relationship between two data sets as appropriate. A p value less or equal to 0.05 will be considered significant.

No adjustment for multiplicity will be applied and missing data will not be replaced.

12.3 Demographics and Other Participant Characteristics

Demographic and other baseline data will be summarized descriptively. All background and demographic data will be listed in detail.

12.4 Efficacy

Primary endpoint of PoC:

The feasibility of imaging apoptotic activity in carotid atherosclerotic plaques using ^{99m}Tc-rhAnnexin V-128 will be determined by the data monitoring committee (visual image review and consensus).

Primary endpoint of Phase II:

Efficacy of ^{99m}Tc-rhAnnexin V-128 planar and SPECT/CT imaging will also be evaluated by determining the prevalence of abnormal ^{99m}Tc-rhAnnexin V-128 scans.

Secondary endpoints:

Descriptive statistics of ^{99m}Tc-rhAnnexin V-128 uptake in control subjects will be presented by areas of interest to assess the background uptake profile.

^{99m}Tc-rhAnnexin V-128 uptake will be related to ultrasound data of plaque echogenicity and echolucency, by direct comparison and by using correlation test and/or diagnostic test performance methods (McNemar test) if appropriate.

^{99m}Tc-rhAnnexin V-128 uptake in carotids will be correlated to its aortic uptake in all participants.

Efficacy analysis of the primary endpoint will be mainly descriptive in nature. Inferential statistics (such as comparisons, correlations...) will be mainly conducted as explorative analyses to serve as the basis for future confirmatory trials.

12.5 Safety

The statistical analysis of safety data will be mainly descriptive in nature.

12.5.1 Adverse Events / Serious Adverse Events

All original AE/SAE terms will be coded using the Medical Dictionary for Regulatory Activities (MedDRA). System organ classes and preferred terms will be used in the analyses. The type and incidence of AEs/SAEs, as well as severity and relatedness to the investigational product will be tabulated.

12.5.2 Laboratory Tests

Descriptive statistics including shift tables will be generated for all laboratory tests performed i.e. the actual values and the changes from pre-injection by cross tabulations (with classes for below, within, and above normal range).

Laboratory data will be analysed with respect to the normal ranges of values provided by the local

laboratory and with respect to levels of change and significance in these values. Abnormal laboratory test results will be tabulated.

13. Adverse Events and other Safety Aspects

13.1 Definition of Adverse Events

An AE is defined as any untoward medical occurrence in a participant and which does not necessarily have a causal relationship with the investigational product. An AE can therefore be any unfavourable and unintended sign (including an abnormal laboratory finding), symptom, or disease, temporally associated with the use of an investigational product, whether or not causally related to the investigational product.

AEs will be reported, if applicable, from the signing of the informed consent until the last study-related procedure.

13.2 Definition of Serious Adverse Events

A SAE is any untoward medical occurrence that at any dose:

- Results in death;
- Is life-threatening;
Note: "life-threatening" refers to an event in which the participant is at risk of death at the time of the event; it does not refer to an event which hypothetically might have caused death if it was more severe;
- Results in persistent or significant disability or incapacity;
- Results in congenital anomaly or birth defect;
- Requires inpatient hospitalization or prolongation of hospitalization.

Serious Adverse Events (SAE) will be defined and reported according to ICH/GCP and Regulatory Standards. SAEs will be reported from the signing of the informed consent and followed until resolution or determined to be not clinically significant.

13.3 Procedure in Case of Pregnancy

Prior to clinical study enrolment, women of childbearing potential must be advised of the importance of avoiding pregnancy during clinical study participation and the potential risks for an unintentional pregnancy. During the clinical study, all women of childbearing potential should use of a reliable means of contraception, and should be instructed to contact the Investigator immediately if they suspect they might be pregnant (e.g. missed or late menstrual period).

The Investigator must report to the Sponsor any pregnancy associated with investigational product exposure including conceptions occurring until 30 days after the IP administration. Appropriate pregnancy follow-up procedures will be considered if indicated. The Investigator should respond in accordance with the reporting procedure for SAEs including information regarding the outcome of pregnancy.

13.4 New Safety Information Affecting the Conduct of the Study

Any information or changes significantly affecting the conduct of the trial and/or increasing the risk to participants will be provided to all investigators, the REB, and Regulatory Authorities.

Depending on the nature of the information or the changes, the protocol and/or the participant information may necessitate an amendment.

13.5 Data Monitoring and Safety

The data collected for this study is observational in design and will not be used for clinical care or clinical decision making. No formal DSMB will be formed. However, the safety data will be part of the review and assessment by the DMC.

14. Termination of the study

Early termination of the study can occur in the following cases:

- When the visual review and analysis of the images of the first 15 patients and 5 normals by the Data Monitoring Committee does not demonstrate the diagnostic potential of the study product in terms of quality or efficacy, the Sponsor may discontinue the clinical study by sending a written notice to the investigator and competent authorities.
- When the Sponsor is aware of new information on matters concerning the safety of the study product, as well as other important information that may affect proper conduct of the clinical study, the Sponsor may discontinue the clinical study and send a written notice of the discontinuation to the investigator and competent authorities.
- If the investigator intends to discontinue participation in the study, the investigator must immediately inform the Sponsor with written notice about the discontinuation and the reason for it.
- The study is stopped by a regulatory authority.
- The Sponsor reserves the right to discontinue the study at any time for any reason by sending a written notice of the discontinuation to the investigator and competent authorities.

15. Operational, Ethical and Administrative Considerations

15.1 Clinical Study Monitoring and Audit

Periodic study monitoring will be conducted by AAA to ensure that participants' human rights, safety, and well-being are protected, that the study is properly conducted in adherence to the current protocol and the principles of ICH GCP as well as Declaration of Helsinki, and that the data reported by the Investigator or designee are accurate, complete, and verifiable with the source documents. The assigned Clinical Study Monitor(s) will monitor the study in accordance with the monitoring guidelines. A copy of the Monitoring Log will be retrieved for the trial master file at the study close-out visits. The designated monitor will have the training and qualifications necessary to provide an appropriate and thorough verification of the study files. During the study, the Investigator will permit the Study Monitor to verify the progress of the study at the centre as frequently as necessary. The Investigator will make the electronic data screens available, provide missing or corrected data, and sign the e-CRF. Key data transcribed into the e-CRF will be reviewed against the source documents. Personal information will be treated as strictly confidential and will not be made publicly available. Any inconsistency between the source data and the data recorded in the e-CRF will be corrected.

The Sponsor will ensure that appropriate Quality Control (QC) steps are included into the different clinical processes to guarantee adequate protection of the study participants and quality of the data.

The Investigator is responsible for the accuracy of the data entered on the e-CRFs. The relevant pages of each e-CRF should be fully completed within 5 working days of the participant's visit to which the data relate, to allow the Clinical Research Associates (CRAs) to review these pages promptly. Sufficient resources must be available to prompt e-CRF completion and collection. Request for clarifications to data (data queries) should be addressed within 5 working days of receipt.

The Investigator shall allow designated CRO/Sponsor representatives, representatives of the REB and regulatory bodies direct access to the source documents (paper or electronic) to verify the data reported in the e-CRFs and data queries (source documents are the originals of any documents used by the Investigator or hospital/institution that allow verification of the existence of the subject and substantiate the integrity of the data collected during the trial). Source documents should be available to support all the data recorded in the e-CRF, unless otherwise specified in the e-CRF and data queries.

The Regulatory Authorities and/or the Ottawa Hospital Science Network Research Ethics Board (OHSN-REB) may review this study. This implies that auditors/inspectors have the right to inspect the study centre(s) at any time during and/or after completion of the study and have access to source documents, including the participant's file.

Study Documents

Source data must be maintained at the study centre to document the existence of the study participants and substantiate the integrity of the collected study data. The author of an entry in the source documents must be identifiable.

The source documents should at least include the following information for each participant:

- Participant identification;
- Documentation of eligibility criteria;
- Consent process, signed and dated ICF;
- Dates of all visits, study procedures documentation;
- Images/scans;
- Investigational product administration time and date;
- Receipt, dispensation and destruction of used/unused investigational product;
- Record of all AEs, SAEs and other safety parameters;
- Date of study completion or reason for early discontinuation (if applicable).

